## 10.6 Required Routine Reporting

### 10.61 Baseline and Adverse Events Evaluations

Pretreatment symptoms/conditions to be graded at baseline and adverse events to be graded at each evaluation.

Grading is per CTCAE v4.0 **unless** alternate grading is indicated in the table below:

System Organ Class (SOC)	Adverse event/Symptoms	Baseline	Each evaluation
Blood and lymphatic system disorders	Anemia		X
Gastrointestinal disorders	# of stools	X	
	Diarrhea		X
	Nausea		X
General disorders and administration site conditions	Fatigue	X	X
Investigations	Neutrophil count decreased		X
	Platelet count decreased		X
Nervous system disorders	Peripheral motor neuropathy	X	X
	Peripheral sensory neuropathy	X	X

10.62 Submit via appropriate MCCC Case Report Forms (i.e., paper or electronic, as applicable) the following AEs experienced by a patient and not specified in Section 10.6:

10.621 Grade 2 AEs deemed *possibly, probably, or definitely* related to the study treatment or procedure.

10.622 Grade 3 and 4 AEs regardless of attribution to the study treatment or procedure.

10.623 Grade 5 AEs (Deaths)

10.6231 Any death within 30 days of the patient's last study treatment or procedure regardless of attribution to the study treatment or procedure.

10.6232 Any death more than 30 days after the patient's last study treatment or procedure that is felt to be at least possibly treatment related must also be submitted as a Grade 5 AE, with a CTCAE type and attribution assigned.

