#### 16.231 Adverse Event Profile

The number and severity of all adverse events (overall and by dose-level) will be tabulated and summarized in this patient population. The Grade 3+ adverse events will also be described and summarized in a similar

fashion. This will provide an indication of the level of tolerance for this treatment combination in this patient group.

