#### 16.232 Toxicity Profile

The term toxicity is defined as adverse events that are classified as either possibly, probably, or definitely related to study treatment. Non-hematologic toxicities will be evaluated via the ordinal CTC standard toxicity grading. Hematologic toxicity measures of thrombocytopenia, neutropenia, and leukopenia will be assessed using continuous variables as the outcome measures (primarily nadir) as well as categorization via CTC standard toxicity grading.

Overall toxicity incidence as well as toxicity profiles by dose level and patient will be explored and summarized. Frequency distributions, graphical techniques and other descriptive measures will form the basis of these analyses.

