**16.42 Secondary Outcome Analyses**

16.421 **Progression-free survival time** is defined as the time from registration to the time of progression or death due to any cause. A progression that occurs during cycle 1 of the phase II portion prior to the addition of lenalidomide will not be considered an event. Patients who are alive and progression-free will be censored on the date of their last disease assessment. Patients who receive subsequent treatment for myeloma before disease progression will be censored on the date of their last disease assessment prior to initiation of the subsequent treatment. The distribution of progression-free survival will be estimated using the method of Kaplan-Meier.

16.422 **Survival time** is defined as the time from registration to death due to any cause. The distribution of survival time will be estimated using the method of Kaplan-Meier.

16.423 **Duration of response** is defined for all evaluable patients who have achieved a confirmed response as the date at which the patient's objective status is first noted to be a sCR, CR, VGPR, or PR to the earliest date progression is documented. The distribution of duration of response will be estimated using the method of Kaplan-Meier.

16.424 **Adverse Events:** All eligible patients that have initiated treatment will be considered evaluable for assessing adverse event rate(s). The maximum grade for each type of adverse event will be recorded for each patient, and frequency tables will be reviewed to determine patterns. Additionally, the relationship of the adverse event(s) to the study treatment will be taken into consideration.

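### Low-grade events of unlisted types are not routinely collected, yet 16.231 and 16.424 plan tables of all adverse events and of maximum grade by type

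*Combined protocol and SAP*

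**What the plan says.** **Collection.** Section 10.61 sets the rule "Pretreatment symptoms/conditions to be graded at baseline and adverse events to be graded at each evaluation" and marks eight terms for every evaluation. Section 10.62 then covers "the following AEs experienced by a patient and not specified in Section 10.6". For those it asks for three things:

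- Grade 2, but only when the event is judged at least possibly related (10.621);
- the severe grades, in these words: "Grade 3 and 4 AEs regardless of attribution to the study treatment or procedure" (10.622);
- deaths within 30 days of last treatment whatever the cause, and later deaths only if at least possibly treatment related (10.623).

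No item in 10.62 asks for Grade 1.

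**Analysis.** Section 16.231 (Phase I): "The number and severity of all adverse events (overall and by dose-level) will be tabulated and summarized in this patient population". A separate summary of the severe grades comes on top of this: "The Grade 3+ adverse events will also be described and summarized in a similar" (sentence cut here). Section 16.232, which defines toxicity as an event at least possibly related to treatment: "Overall toxicity incidence as well as toxicity profiles by dose level and patient will be explored and summarized". Section 16.424 (Phase II): "The maximum grade for each type of adverse event will be recorded for each patient, and frequency tables will be reviewed to determine patterns". None of these sections mentions the collection threshold.

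**The concern.** The safety profile is a secondary objective in both phases (2.21 and 2.23). If the forms follow 10.6 and the tables follow Section 16, a patient whose only rash is Grade 1 is counted as having had no rash. This matters for ibrutinib because the Background itself describes several of its effects as mostly low grade: rash (1.97), minor bleeding such as epistaxis and petechiae (1.91), and vomiting and constipation (1.94). None of these is on the 10.61 list.

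There are two further consequences. Within one table, the Grade 2 column for an unlisted type holds related events only, while the Grade 3 and 4 columns hold events of any attribution. And when listed and unlisted types are compared to look for patterns, part of the difference reflects how they were collected.

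**Working it through.** **1. Routine collection during treatment, by grade.** The eight terms in 10.61 are anemia, diarrhea, nausea, fatigue, neutrophil count decreased, platelet count decreased, peripheral motor neuropathy and peripheral sensory neuropathy. Number of stools is a baseline item only.

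| Worst grade | Eight listed terms | All other terms |
|---|---|---|
| 1 | all | not asked for |
| 2 | all | only if at least possibly related |
| 3 or 4 | all | all |

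**2. Other routes.** Under 10.41, a Grade 1 or 2 event with hospitalization of at least 24 hours needs an expedited report, and 10.1(f) sends every expedited event to the routine data as well. Under 10.8 and 10.8.1, central nervous system hemorrhage of any grade and serious bleeding of any grade go to the drug supplier on serious-event timelines. Ordinary low-grade events use neither route.

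**3. Late window.** Footnote k of the test schedule limits late events to Grade 3 or higher at least possibly related, plus deaths. For deaths after 30 days, 10.6232 requires at least possible relatedness. So Grade 3+ of any attribution is complete only during active treatment.

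**4. Set against the analysis text.** In 16.231 the table of all events cannot mean Grade 3+, because Grade 3+ is a separate, additional summary. Section 16.424 sets no limit by grade or attribution. Section 16.232 counts related events only. Since related Grade 2 and above is submitted for every type during treatment, it loses only related Grade 1 events of unlisted types.

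**5. How many types.** Section 15.17 names 19 very common ibrutinib toxicities. Six match the list: neutropenia, thrombocytopenia, anemia, diarrhea, nausea and fatigue. That leaves 19 − 6 = 13: constipation, vomiting, decreased appetite, peripheral edema, pyrexia, pneumonia, upper respiratory tract infection, arthralgia, back pain, headache, cough, dyspnea and rash.

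**6. Size.** For an unlisted type, let g1, g2 and g3 be the shares of patients with worst grade 1, 2 and 3 or higher, and r the share of the Grade 2 patients whose event is judged related. Ignoring hospitalized low-grade events:

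- true any-grade rate = g1 + g2 + g3
- tabulated rate = r·g2 + g3
- shortfall = g1 + (1 − r)·g2

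The documents give none of these shares. The shortfall is zero if g1 = 0 and r = 1, and it is the whole rate if all events are Grade 1. As one assumed mix, take g1 = 0.35, g2 = 0.20, g3 = 0.05 and r from 0.3 to 0.7. The true rate is 0.60. The tabulated rate is 0.20 × 0.3 + 0.05 = 0.11 to 0.20 × 0.7 + 0.05 = 0.19. In 34 patients that is 20.4 against 3.7 to 6.5. This shows the mechanism and is not an estimate.

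**7. Effect on a stated figure.** Section 16.21 says six patients show a toxicity of 25% incidence with probability 82%: 1 − 0.75^6 = 0.822, which reproduces. If only 75%, 50% or 25% of patients with an unlisted toxicity reach the forms (assumed), the recorded incidence is 18.75%, 12.5% or 6.25%. The chance that the table shows it at all is then 1 − 0.8125^6 = 0.71, 1 − 0.875^6 = 0.55 or 1 − 0.9375^6 = 0.32.

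**8. What does not depend on low grades.** Dose-limiting toxicity in 7.32 rests on Grade 3 or higher events or on treatment delay. The stopping rules in 16.52 use those toxicities and related Grade 4 or higher non-hematologic events. The response endpoint uses disease measurements.

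**The case against.** The strongest reply is that collection thresholds are ordinary in oncology, that all adverse events can be read as all recorded ones, and that nothing in Section 16 promises an any-grade rate. Section 16.23 calls the Phase I analyses exploratory, and 16.424 says relationship to treatment will be considered. The threshold itself is indeed not the fault. What remains is that neither table is defined by what is collected, so a reader will take a missing Grade 1 or 2 entry as no event.

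Other parts of the reply stand:

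- A reader might infer that Grade 1 events of unlisted types never reach the data. Hospitalized ones do, so the statement holds only for routine reporting.
- A reader might extend the mixed-attribution problem to 16.232. That section is already limited to related events, so there is no case for removing its overall toxicity incidence; it needs only a stated grade limit.
- The case report form packet, to which 18.1 refers, is not in the documents and could ask for more than 10.6 requires.
- Five of the 13 unlisted terms (vomiting, appetite, shortness of breath, constipation, rash) have 0 to 10 ratings in the MDASI-MM. These are periodic and are not CTCAE grades, so they do not fill the tables.

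**Conclusion.** The mismatch is real but limited. As 10.6 is written, any-grade rates in 16.231 and 16.424 would be understated for unlisted types, including 13 of the 19 very common ibrutinib toxicities, and the grade columns for those types would mix attribution rules. In 16.232 only related Grade 1 events of unlisted types are missed. This assumes that the forms ask for no more than 10.6 does.

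The amount cannot be computed. A contrast such as 60% against 11–19% follows only from the assumed grade mix above, and the documents do not support it as a finding. Nor do they support an inference that dose finding or safety monitoring is compromised: dose-limiting toxicities, stopping rules, on-treatment Grade 3+ summaries and the response endpoint are untouched. The point is worth correcting for the safety objectives.

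**What to change.** In 16.231 and 16.424, replace the tables of all adverse events and of any-grade maximum with tables that match collection:

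- (a) Grade 3 or higher regardless of attribution, all types, during active treatment;
- (b) Grade 2 or higher at least possibly related, all types, during active treatment;
- (c) all grades for the eight 10.61 terms only;
- (d) late events separately, as collected under footnote k and 10.623: Grade 3 or higher at least possibly related, and deaths.

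Give no any-grade rate for unlisted types. In 16.232, keep the overall toxicity incidence but define it, for unlisted types, as related Grade 2 or higher. If the form packet does ask for more, state that in 10.62 and align the tables with it.

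The change is to wording only and needs no new data or visits. The cost is that the report no longer claims an any-grade profile for unlisted events.

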## 10.7 Late Occurring Adverse Events

Refer to the instructions in the Forms Packet (or electronic data entry screens, as applicable) regarding the submission of late occurring AEs following completion of the Active Monitoring Phase (i.e., compliance with Test Schedule in Section 4.0).

## 10.8 Adverse Events of Special Interest (AESI)

Specific adverse events, or groups of adverse events, will be followed as part of standard safety monitoring activities. These events (regardless of seriousness) will be reported to Pharmacyclics Drug Safety per SAE reporting timelines.

### 10.8.1 Major Hemorrhage

Major hemorrhage is defined as any of the following:

- Any treatment-emergent hemorrhagic adverse events of Grade 3 or higher\*. Any treatment-emergent serious adverse events of bleeding of any grade
- Any treatment-emergent central nervous system hemorrhage/hematoma of any grade

\*All hemorrhagic events requiring transfusion of red blood cells should be reported as grade 3 or higher AE per CTCAE v4.0.

Events meeting the definition of major hemorrhage will be captured as an event of special interest according to Section 10.8 above.

## 11.0 Treatment Evaluation

The International Myeloma Working Group (IMWG) uniform response criteria will be used to assess response to therapy.

### 11.1 Terms and definitions

- **Monoclonal protein:** synonyms include M-spike, M-protein and myeloma protein, paraprotein, M-component.

Serum Monoclonal protein level is quantitated using densitometry on SPEP except in cases where the SPEP is felt to be unreliable.

- Monoclonal protein migrating in the β-region (usually IgA Monoclonal protein)
- Cases in which the Monoclonal protein is so large and narrow on agarose (some specimens >4 g/dL) that they underestimate the actual immunoglobulin level (by greater than 1500 mg/dL) due to technical staining properties of the agarose gel.
- Cases in which there are multiple peaks of same Monoclonal protein (aggregates or dimers)

If SPEP is not available or felt to be unreliable (above examples) for routine Monoclonal protein quantitation, then quantitative immunoglobulin levels derived from nephelometry or turbidometry can be accepted. However, this must be explicitly reported at baseline, and only nephelometry can be used for that patient to assess response. SPEP derived Monoclonal protein values and quantitative nephelometric immunoglobulin values cannot be used interchangeably.

Urine Monoclonal protein measurement is estimated using 24-h UPEP only. Random or 24 h urine tests measuring kappa and lambda light chain levels are not reliable and are not recommended.

**FLC estimation** is currently carried out using the serum FLC assay (Freelite, The Binding Site Limited, UK). Patients with kappa/lambda FLC ratio  $<0.26$  are defined as having monoclonal lambda FLC and those with ratios  $>1.65$  as having a monoclonal kappa FLC. The monoclonal light chain isotype is considered the involved FLC isotype, and the opposite light chain type as the uninvolved FLC type.

- **Response terms:** The following response terms will be used: stringent Complete Response (sCR), complete response (CR), very good partial response (VGPR), partial response (PR), Minimal Response (MR), stable disease (SD), and progressive disease (PD).

In addition, for each response category, there will be an “unconfirmed” response category, which will be for internal use, for the purpose of guiding decision making and test ordering. These designations will be applied at the time of the first measurement at which the quantitative aspect of the response category has been satisfied without the confirmation step having been satisfied. The designation “u” will precede the standard abbreviations, and will include usCR, uCR, uVGPR, uPR, uMR, uPD.

- **Measurable disease:** Patients who have a measurable serum or urine Monoclonal protein.
- Serum Monoclonal protein  $\geq 1$  g/dl
- Urine Monoclonal protein  $\geq 200$  mg/24 h
- Serum FLC assay: Involved FLC level  $\geq 10$  mg/dl provided serum FLC ratio is abnormal
- Bone marrow plasma cells  $\geq 30\%$

The serum free light chain (FLC) assay is of particular use in monitoring response to therapy in patients who have oligo-secretory or non-secretory disease and **should be used in assessing response only if the baseline serum and/or urine M proteins are not “measurable” as above, and the baseline level of the involved FLC is “measurable.”** When using this assay, it is important to note that the FLC levels vary considerably with changes in renal function and in patients with renal insufficiency, the levels of both the kappa and lambda may remain elevated, but the ratio normalizes with achievement of CR. Thus, both the level of the involved and the uninvolved FLC isotype (i.e., the involved/uninvolved ratio or involved-uninvolved difference) should be considered in assessing response. *Patients included on the study on the basis of FLC alone (i.e., no measurable serum/urine Monoclonal protein) should be the only ones who are evaluated using FLC response criteria. The others should follow usual criteria and ignore FLC results* with the exception of defining stringent complete response.

- **Evaluable disease:** Patients who do not have a “measurable” serum Monoclonal protein, serum free light chain, or urine Monoclonal protein.
- **Oligosecretory myeloma:** Patient with multiple myeloma who has NEVER had “measurable” serum Monoclonal protein or urine Monoclonal protein, but has had a detectable Monoclonal protein in his/her serum and/or urine and/or measurable serum free light chain.

- **Non-secretory myeloma:** Patient with multiple myeloma who has NEVER had a detectable Monoclonal protein in his/her serum and/or urine.

### 11.2 Clarification of test indications

Listed below are the minimal required tests required to assess response based on the characteristics of their disease at on study.

Table 11.2				
Tests Required To Assess Response (Must Be Done At Each Disease Measurement Visit except as indicated 				
On Study Baseline Value	SPEP 	24 hr UPEP 	Ig FLC	BM Bx
Serum Monoclonal protein $\geq 1$ g/dl, and urine Monoclonal protein $\geq 200$ mg/24 hrs	X	X		
Serum Monoclonal protein $\geq 1$ g/dl, but urine Monoclonal protein $< 200$ mg/24 hrs	X			
Serum Monoclonal protein $< 1$ g/dl, and urine Monoclonal protein $\geq 200$ mg/24 hrs		X		
Serum Monoclonal protein $< 1$ g/dl, urine Monoclonal protein $< 200$ mg/24 hrs, but involved Ig FLC is $\geq 10$ mg/dL			X	
Serum Monoclonal protein $< 1$ g/dl, urine Monoclonal protein $< 200$ mg/24 hrs, involved Ig FLC is $< 10$ mg/dL, bone marrow $\geq 30\%$ plasma cells				X 

 SPEP, UPEP, Immunofixation studies of both serum and urine, and Bone marrow biopsy are required to document CR regardless of registration values, and in addition FLC measurement and bone marrow immunophenotyping is required to document sCR. SPEP and UPEP are required to document VGPR regardless of registration values.

 For serum measurable patients, 24 hour urine does not need to be confirmed (i.e. repeated after documented response) for any response category

 At a minimum, a bone marrow biopsy should be repeated every 3 months until documented response. Bone marrow biopsy results do not need to be repeated after documented response.

 If serum Monoclonal proteinprotein is being followed by quantitative immunoglobulin levels derived from nephelometry or turbidometry, quantitative immunoglobulins are required. SPEP is only required to document CR or VGPR.

### 11.3 Confirmed response

In order to be classified as a hematologic response, confirmation of serum M- protein, serum immunoglobulin free light chain (when primary determinant of response) and urine M- protein (when primary determinant of response) results must be made by verification on two consecutive determinations.

- Bone marrow aspirate and biopsy are **only** required to document CR or sCR, except for patients with evaluable disease **only**, where a bone marrow is required to document all response categories including progression. However, a second confirmatory bone marrow is **not** required to confirm response in any case.
- Radiographic studies are not required to satisfy these response requirements;

however, if radiographic studies were performed there should be no evidence of progressive or new bone lesions.

Appropriate tests required to document and confirm response are listed in Table 11.2

#### 11.4 Bone progression

Caution must be exercised to avoid rating progression on the basis of variation of radiologic technique alone. Compression fracture does not exclude continued response and may not indicate progression. When progression is based on skeletal disease alone, it should be discussed with the Study Chair before removing the patient from the study.

#### 11.5 Response and Progression

Criteria for response and progression are listed in Table 11.5. Progressive disease for all patients as defined in Table 11.5.

NOTE: For patients that have progressive disease on ibrutinib and dexamethasone during cycle 1, baseline values for the assessment of response to the combination of ibrutinib, dexamethasone, and lenalidomide will be defined as the values at the end of cycle 1.

Table 11.5

CATEGORY	RESPONSE CATEGORY a
Stringent Complete Response (sCR) b	
 
• CR as defined plus
 
• Normal FLC ratio and
 
• Absence of clonal PCs by immunohistochemistry or 2- to 4- color flow cytometry i
 

Complete Response (CR) b	
 
• Negative immunofixation of serum and urine c and
 
• Disappearance of any soft tissue plasmacytoma and
 
• <5% PCs in Bone Marrow and
 
• If the only measurable disease is FLC, a normal FLC ratio d
 

Very Good Partial Response (VGPR)	
 
• Serum and urine Monoclonal protein detectable by immunofixation but not on electrophoresis c or
 
• ≥90% reduction in serum Monoclonal protein and urine Monoclonal protein <100 mg/24 hc
 
• If the only measurable disease is FLC, a >90% reduction in the difference between involved and uninvolved FLC levels
 

Partial Response (PR)	
 
• If present at baseline, ≥50% reduction of serum Monoclonal protein and reduction in 24-hour urinary Monoclonal protein by ≥90% or to <200 mg/24hrsc
 
• If the only measurable disease is FLC, a ≥50% reduction in the difference between involved and uninvolved FLC levels
 
• If the only measurable disease is BM, a ≥50% reduction in BM PCs (provided the baseline PCs was ≥30%)
 
• If present at baseline, ≥50% reduction in the size of soft tissue plasmacytomas
 

Minor Response (MR)	
 
• If present at baseline, ≥25% but ≤49% reduction of serum M protein and reduction in 24-hour urine Monoclonal protein by 50-89% which still exceeds 200mg/24 hours c and
 
• If present at baseline, 25-49% reduction in the size of soft tissue plasmacytoma and
 
• No increase in the size or number of lytic bone lesions (development of compression fracture does not exclude response)
 

Progressive Disease	Increase of 25% from lowest value in any of the following f,g :

Table 11.5

CATEGORY	RESPONSE CATEGORY a
(PD) b, h	
 
• Serum Monoclonal protein (absolute increase must be <math>\geq 0.5</math> g/dL) and/or
 
• Urine Monoclonal protein (absolute increase must be <math>\geq 200</math> mg/24 hrs) and/or
 
• If the only measurable disease is FLC, the difference between involved and unininvolved FLC levels (absolute increase must be <math>>10</math> mg/dL) and/or
 
• If the only measurable disease is BM, bone marrow PC percentage (absolute increase must be <math>\geq 10\%</math>) e
 
 
Or any one or more of the following:
 
 
• Development of new bone lesion or soft tissue plasmacytoma or definite increase in the size of existing bone lesions or soft tissue plasmacytoma
 
• Development of hypercalcemia (corrected serum calcium <math>>11.5</math> mg/dL) that can be attributed solely to the PC proliferative disorder
 

Stable Disease (SD)	Not meeting criteria for sCR, CR, VGPR, PR, MR or PD

a All response categories require two consecutive assessments (sCR, CR, VGPR, PR, MR, PD) made at any time before the institution of any new therapy; sCR, CR, VGPR, PR, MR and SD categories also require no known evidence of progressive or new bone lesions if radiographic studies were performed. Radiographic studies are not required to satisfy these response requirements. Bone marrow assessments need not be confirmed. Each category, except for stable disease, will have a working subcategory of "unconfirmed" [prefix 'u'] to designate first time point at which response category MAY have been achieved if confirmed.

b CR patient will need to progress at the same level as VGPR and PR patients to be considered a PD. A positive immunofixation alone is not sufficient.

c If more than one M protein spike meets the criteria for measurable disease at baseline, then both need to be followed for response. Otherwise, only follow the measurable M protein spike for response.

d In patients in whom the only measurable disease is by serum FLC levels: CR in such patients indicates a normal FLC ratio of 0.26-1.65 in addition to the CR criteria listed above.

e Bone marrow criteria for PD are only to be used in patients without measurable disease by M protein and by FLC;

f A "25% increase" refers to M protein, FLC and bone marrow results and does not refer to bone lesions, soft tissue plasmacytoma or hypercalcemia. The lowest value does not need to be a confirmed value. If the lowest serum Monoclonal protein is  $\geq 5$  g/dL, an increase in serum Monoclonal protein of  $\geq 1$  g/dL is sufficient to define disease progression.

g In the case where a value is felt to be a spurious result per physician discretion (for example, a possible lab error), that value will not be considered when determining the lowest value.

h Progressive disease should be confirmed. However, treatment may be discontinued for progressive disease that is unconfirmed per physician discretion. In this case, an objective status of PD should be entered on the measurement form and progressive disease should be reported on the event monitoring form.

i Presence/absence of clonal cells is based upon the k/l ratio. An abnormal k/l ratio by immunohistochemistry requires a minimum of 100 plasma cells for analysis. An abnormal ratio reflecting presence of an abnormal clone is k/l of 4:1 or 1:2.

